### 3.4.2.5 Overall Survival

Overall survival (OS) is defined as the time from the first dose of investigational product until death due to any cause. For patients who are alive at the time of analysis, OS will be censored on the last date when patients are known to be alive. The last date for each individual subject is defined as the latest among the following dates recorded on the case report forms (CRFs):

- AE start, stop, and change dates
- Admission and discharge dates of hospitalization
- Study treatment date
- Date of last contact, withdrawal consent, refuse to be followed up, or last known alive on end of treatment, end of study, and survival status/follow-up CRFs
- Laboratory test dates including (but not limited to) hematology, chemistry, urinalysis, coagulation, tumor biopsy, immunoglobulin, pharmacokinetics CCI [REDACTED] CCI [REDACTED].
- Disease assessment dates on RECIST CRF
- Date of visit, vital signs, ECOG, ECG, and physical examination
- Start and stop dates of alternative anticancer treatment
- Dates on quality of life questionnaire CRFs
- Start and end date of concomitant medication and surgical/medical procedure

OS is defined in months as follows:

$$\text{OS (months)} = (\text{Date of death or censoring} - \text{Date of the first dose of investigational product} + 1) / (365.25/12).$$

The number and percentage of patients experiencing a OS event and Kaplan-Meier plots of OS will be presented by treatment group. The median OS and its 95% CI will be estimated using the Kaplan-Meier method. The proportion of subjects alive at time points of interest (such as 3 months and 6 months) and associated 95% CI will be estimated using the Kaplan-Meier method.

[figure not shown]
### 3.4.3 Handling of Dropouts and Missing Data

In general, missing data are not imputed for statistical analysis. Guidance regarding the handling of dropouts and missing data and censoring will apply uniformly to all efficacy analyses resulting from an application of RECIST 1.1 to investigator assessed tumor measurements (details are specified in the corresponding endpoint section and Appendix 7.1). For investigator reported outcomes, analyses will present outcomes reported by the investigator without consideration of missing data or censoring rules.

### 3.4.4 Subgroup Analyses

When appropriate (e.g. sufficient sample size in each subgroup), the analysis of OR and DC may be performed by T790M status (gene mutation vs. no gene mutation) at baseline (determined by a central lab) in archival and/or fresh tumor biopsies.

### 3.4.5 Exploratory CCI ██████████ Analyses

### 3.4.6 Other Efficacy Analyses

#### 3.4.6.1 Change from Baseline in Tumor Sizes

The percent change from baseline in target lesion sum of diameters (longest for non-nodal lesions, short axis for nodal lesions) will be calculated at each adequate post-baseline disease assessment. The percent change from baseline in target lesion sum of diameters is defined as follows:

$$100 * (\Sigma \text{ Diameters at DA X} - \Sigma \text{ Diameters at BL}) / (\Sigma \text{ Diameters at BL}).$$

DA = Disease Assessment; BL = Baseline.

The percent change from baseline in target lesion sum of diameters will be presented by subject using spider plots. The best percent change from baseline in target lesion sum of diameters is defined as the largest reduction or smallest increase (in the case where a

reduction does not occur) from baseline observed over all post-baseline disease assessments prior to the initiation of subsequent anticancer treatment. The best percent change from baseline will be presented using waterfall plots. Target lesion measurements and sum of diameters will be listed by disease assessment and subject.

### 3.5 CCI

CCI

## 3.6 Safety Analyses

All safety analyses will be performed based on as-treated population, unless otherwise specified.

### 3.6.1 RP2D Evaluation

The Recommended Phase 2 dose (RP2D) evaluation will be based on the DLT Evaluable Population. The number and percentage of subjects with DLTs will be presented by dose level. The RP2D level will be indicated in the summary.

### 3.6.2 Adverse Events and Serious Adverse Events

Treatment-emergent adverse event (TEAE) is defined as events present at baseline that worsen in intensity after administration of study investigational product or events absent at baseline that emerge after administration of study investigational product. All TEAEs that occurred on and after first dose to 28 days after last dose of IP will be listed and summarized.

TEAEs will be summarized by system organ class and preferred term using the Medical Dictionary for Regulatory Activities (MedDRA) dictionary, severity graded according to National Cancer Institute Common Terminology Criteria for Adverse Events Version 4.03 (NCI CTCAE, v4.03) (Grade 1, Grade 2, Grade 3, Grade 4, and Grade 5), and relationship to study drug.

Subjects will be counted only once for each preferred term, once for each system organ class, and by the highest severity, regardless of how many events the subject experienced. TEAEs that result in permanent discontinuation of investigational product(s) or death will be summarized descriptively and listed.

The TEAE summaries to be provided are listed in [Table 3.6.2-1](#)

**Table 3.6.2-1 Treatment-emergent Adverse Events and Serious Adverse Events to be Summarized**

Summary	Population
Rate summary of all Treatment Emergent Adverse Events	As-treated
Treatment Emergent Adverse Events / Related TEAEs	As-treated
Treatment Emergent Adverse Events by Highest Severity / Related TEAEs by Highest Severity	As-treated
Treatment Emergent Adverse Events Sorted by Frequency / Related Treatment Emergent Adverse Events Sorted by Frequency	As-treated
Grade 3 or Grade 4 TEAEs / Related Grade 3 or Grade 4 TEAEs	As-treated
Serious TEAEs / Related Serious TEAEs	As-treated
Serious TEAEs by Serious Adverse Criteria	As-treated
Treatment Emergent Adverse Events Resulting in Permanent Discontinuation of Study Drug /Related TEAEs Resulting in Permanent Discontinuation of Study Drug	As-treated
Treatment Emergent Adverse Events Resulting in Dose Delay or Omission or Dose Interruption / Related TEAEs Resulting in Dose Delay or Omission or Dose Interruption	As-treated
Treatment Emergent Adverse Events Resulting in Death / Related TEAEs Resulting in Death	As-treated

The AEs occurring from the signing of the informed consent and prior to the initiation of study investigational product will be listed.

### 3.6.3 Adverse Events of Special Interest

Per protocol section 5.3, Adverse Events of Special Interest for oleclumab include the following:

- Infusion-related Reactions
- Cardiac Chest Pain, Transient Ischemic Attack, and Thromboembolism
- Edema
- Immune Complex Disease

Adverse Events of Special Interest for Osimertinib include:

- Interstitial Lung Disease/Pneumonitis
- QTc prolongation and Arrhythmias
- Changes in cardiac contractility

Adverse Events of Special Interest for AZD4635 include:

- Seizures

Other categories may be added or existing terms may be modified as necessary. Preferred terms used to identify each AESI group will be listed before data base lock. AESI grouping summary tables will be produced and may also show the individual preferred terms within each AESI grouping.

AESI summaries to be provided are listed below. For patients on Arm A, two sets of AESI summaries will be prepared: one for oleclumab and the other for osimertinib; for patients on Arm B, two sets of AESI summaries will be prepared: one for oleclumab and the other for AZD4635;

- All AESI
- All AESI by highest severity
- Treatment related AESI
- Treatment related AESI by highest severity

#### **3.6.4 AEs During Which Systemic Steroids, Endocrine Therapy, or Other Immunosuppressants Were Administered**

AEs during which systemic steroids, endocrine therapy, or other immunosuppressants were administered will be programmatically identified by searching for dates of initiation of these agents and comparing to the onset dates and resolution dates of AEs for individual subjects. The concomitant medications administered to subjects will be identified by searching the clinical database for select ATC codes to identify systemic steroids, endocrine therapy and other immunosuppressants. See a list of select ATC codes in the durvalumab imAE Charter. The last version of the imAE charter before the DCO (Data Cut Off) date for analysis will be used.

Summaries of AESIs during which systemic steroids, endocrine therapy, or other immunosuppressants were administered as listed in the imAE charter will be provided.

#### **3.6.5 Immune-mediated Adverse Events (imAE)**

To fully characterize the AEs during which systemic steroids, endocrine therapy, or other immunosuppressants were administered, the Sponsor will perform medical review of those AEs and classify them as immune-mediated AEs (imAEs) or not imAEs. See further details in the durvalumab imAE Charter.

Immune-mediated AEs will be defined as are defined as AEs of an immune nature (ie, inflammatory) in the absence of a clear alternative etiology.

imAEs will be derived by first programmatically identifying AEs during which systemic steroids, endocrine therapy, or other immunosuppressants were administered as outlined above in Section 3.6.4. A further clinical evaluation of all such events will be made to ensure there was no clear alternate etiology before classifying them as imAEs for the purpose of analysis and reporting.

The imAEs will be summarized in the same manner as for the summaries for AESI described above in Section 3.6.3 and Section 3.6.4.

In addition, analyses of time to first onset imAE, time to resolution of imAE, and systemic steroid use for imAE may be provided by imAE group. See further details in the imAE Charter with respect to derivation rules associated with these endpoints and their analyses.

### **3.6.6 Deaths and Treatment Discontinuations due to Adverse Events**

Refer to Section 3.6.2.

### **3.6.7 Clinical Laboratory Evaluation**

Laboratory tests will be grouped according to hematology, serum chemistry, urinalysis, and thyroid function tests (TSH, free thyroxine T4). For all continuous laboratory assessments, absolute value and change from baseline will be summarized for each scheduled assessment, “worst-case” (nadir and/or zenith) on treatment, and the last assessment on-treatment using descriptive statistics. Laboratory abnormalities with toxicity grades according to the NCI CTCAE 4.03 will be derived according to laboratory values. Shift tables from baseline to worst toxicity grade on treatment will be presented. Separate summaries indicating hyper- and hypo- directionality of change will be produced, where appropriate. In addition, the number and percentage of subjects experiencing at least 2-Grade shift, and any shift to a worst post-baseline toxicity Grade of 3 to 4 from baseline will be summarized. For each lab test condition, percentages are calculated based on the number of treated subjects who have a baseline and at least one post-baseline assessment. In the shift table analysis, for a given subject, if a subject has both missing and non-missing CTCAE grades for one laboratory test, the missing CTCAE grade of that laboratory test will be treated as the lowest grade.

Laboratory abnormalities with toxicity grades according to the NCI CTCAE 4.03 will be derived for the following parameters:

Hematology: Anemia (Hemoglobin decreased), White Blood Cell decreased, Neutrophils decreased, Platelets decreased, Lymphocytes decreased

Serum chemistry: Alanine Amino Transferase (ALT) increased, Aspartate Amino Transferase (AST) increased, Alkaline Phosphatase (ALP) increased, Total bilirubin increased, Creatinine increased, Magnesium hypo and hyper, Sodium hypo and hyper, Potassium hypo and hyper, Corrected calcium hypo and hyper, Glucose hypo and hyper, Cholesterol high, GGT increased, Lipase increased, Amylase increased.

For thyroid function tests (TSH, free thyroxine T4) with no CTCAE grading, summary table of shifts from baseline relative to the normal range in thyroid function will be provided. Number of subjects will be summarized for those with normal baseline and at least one post-baseline TSH value below LLN and a concurrent free Thyroxine above the ULN and those with normal baseline and at least one post-baseline TSH value above ULN and a concurrent free Thyroxine below the LLN.

Liver Function Parameters

Subjects with elevated post-baseline ALT, AST or Total Bilirubin that fall into the following categories will be identified. Number and percentage of these subjects will be tabulated.

Liver Function Parameters	Category
ALT	
 
• <math>\geq 3 \times - \leq 5 \times \text{ULN}</math>
 
• <math>> 5 \times - \leq 8 \times \text{ULN}</math>
 
• <math>> 8 \times - \leq 10 \times \text{ULN}</math>
 
• <math>> 10 \times - \leq 20 \times \text{ULN}</math>
 
• <math>> 20 \times \text{ULN}</math>
 

AST	
 
• <math>\geq 3 \times - \leq 5 \times \text{ULN}</math>
 
• <math>> 5 \times - \leq 8 \times \text{ULN}</math>
 
• <math>> 8 \times - \leq 10 \times \text{ULN}</math>,
 
• <math>> 10 \times - \leq 20 \times \text{ULN}</math>
 
• <math>> 20 \times \text{ULN}</math>
 

Total bilirubin	
 
• <math>\geq 2 \times - \leq 3 \times \text{ULN}</math>
 
• <math>> 3 \times - \leq 5 \times \text{ULN}</math>
 
• <math>> 5 \times \text{ULN}</math>
 

ALT or AST	
 
• <math>\geq 3 \times - \leq 5 \times \text{ULN}</math>
 
• <math>> 5 \times - \leq 8 \times \text{ULN}</math>
 
• <math>> 8 \times - \leq 10 \times \text{ULN}</math>,
 
• <math>> 10 \times - \leq 20 \times \text{ULN}</math>
 
• <math>> 20 \times \text{ULN}</math>
 

Potential Hy's law	
 
• (AST <math>\geq 3 \times \text{ULN}</math> or ALT <math>\geq 3 \times \text{ULN}</math>) and (Total Bilirubin <math>\geq 2 \times \text{ULN}</math>)a
 

Liver Function Parameters	Category
---------------------------	----------

ULN: upper limit of normal range.

a: Total Bilirubin  $\geq 2 \times \text{ULN}$  is defined as at least one case of post-dose TBL  $\geq 2 \times \text{ULN}$  occurred at the same day or after the first incidence date of ALT or AST  $\geq 3 \times \text{ULN}$  post treatment.

Individual subject data where elevated ALT or AST plus total bilirubin fall into the “Potential Hy’s law” will be listed.

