### 3 STATISTICAL METHODS

#### 3.1 General Considerations

Tabular summaries will be presented by treatment group. Categorical data will be summarized by frequency distribution (number and percentage of subjects falling within each category). Continuous variables will be summarized by descriptive statistics including N, mean, standard deviation, median, and range (minimum and maximum). All available data will be used and thus missing data will not be imputed. In general, subjects with missing data for a parameter will be excluded from the summary of this parameter. Tables will be supported by data listings showing the original data forming the basis for the summaries. Data listings will be sorted by treatment group, subject number and date collected where applicable.

In general, unless stated otherwise, two-sided confidence intervals will be produced at 95%. Baseline values will be defined as the last valid assessment prior to the first administration of investigational product.

The data analyses will be conducted using the SAS® System (SAS Institute, Inc., Cary, NC, USA) Version 9.3 or above. All analysis outputs will be validated according to MedImmune SAS programming standards and MedImmune validation procedures.

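### The laboratory shift-table rule sets a missing CTCAE grade to the lowest grade without limiting its scope, so an underivable baseline grade can produce a false shift

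*SAP*

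**What the plan says.** SAP Section 3.6.7 derives grades from the results themselves: "Laboratory abnormalities with toxicity grades according to the NCI CTCAE 4.03 will be derived according to laboratory values". It then plans two kinds of output from them. The first is a shift table: "Shift tables from baseline to worst toxicity grade on treatment will be presented". The second is a count of larger shifts: "the number and percentage of subjects experiencing at least 2-Grade shift, and any shift to a worst post-baseline toxicity Grade of 3 to 4". Hypo and hyper directions are summarised separately where appropriate; the tests listed with both directions are magnesium, sodium, potassium, corrected calcium and glucose.

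Two adjacent sentences then set the handling of incomplete data. On the denominator, "percentages are calculated based on the number of treated subjects who have a baseline and at least one post-baseline assessment". The other concerns the shift analysis and a subject who is graded at some points on a test but not at others; there, "the missing CTCAE grade of that laboratory test will be treated as the lowest grade". The section does not say which grade counts as lowest, whether the baseline grade is covered, or whether the rule is meant only for hypo/hyper tests.

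SAP Section 3.1 sets the general position: "All available data will be used and thus missing data will not be imputed". It adds that subjects lacking data for a parameter are, in general, left out of that parameter's summary. It also fixes the baseline: "Baseline values will be defined as the last valid assessment prior to the first administration of investigational product".

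**The concern.** A shift compares two grades. If the baseline grade is unknown and is entered as the lowest, any abnormality the subject already had is counted as arising on treatment. If all post-baseline grades are unknown and are entered as the lowest, the subject appears not to have worsened when nothing is known. The two errors run in opposite directions, and the shift table alone would not show which grades were filled in. Safety and tolerability is a primary objective in both parts (SAP Section 2.1.1). With arms of about 46 and 52 subjects, one wrong classification is visible in a percentage. Two programmers could also implement the sentence differently.

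**Working it through.** The SAP gives no figure for this rule, so there is none to reproduce. The check is one of logic, taking lowest grade to mean Grade 0 and grades to run from 0 to 4.

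**Step 1: some post-baseline grades missing, at least one present.** The table uses the worst grade. For observed grades g1 to gk, max(g1, ..., gk, 0) = max(g1, ..., gk). With three visits, each either missing or graded 0 to 4, the patterns with at least one missing and one observed grade number 3 × 25 (one missing) + 3 × 5 (two missing) = 90. Counting missing as 0 leaves the maximum unchanged in 90 of 90. The rule has no effect here.

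**Step 2: baseline grade missing, post-baseline graded.** The subject has both missing and non-missing grades, so the literal rule applies. Setting baseline to 0 and listing all 5 × 5 = 25 pairs of true baseline and observed worst grade gives:

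| Summary | Flagged | Truly a shift | False |
|---|---|---|---|
| At least 2 grades | 3 × 5 = 15 | 6 (0→2, 0→3, 0→4, 1→3, 1→4, 2→4) | 9 |
| Worsening to Grade 3-4 | 2 × 5 = 10 | 7 | 3 (3→3, 4→3, 4→4) |

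For example, a subject truly at Grade 2 before treatment and at worst Grade 2 on treatment has a shift of 0 but is reported with a shift of 2. These are counts of possible pairs, not expected rates.

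**Step 3: baseline graded, every post-baseline grade missing.** The worst grade becomes 0, so no worsening is shown whatever happened.

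**Step 4: who can be affected.** The denominator sentence requires a baseline and a post-baseline assessment, not a derivable grade. Since grades are derived from results, an assessment can exist without one, for instance if a needed reference limit is missing. Such subjects stay in the denominator and receive a filled-in grade. Subjects with no baseline assessment are outside the denominator; if the rule were nevertheless applied to them, they would enter the numerator only.

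**Step 5: size per subject.** Arm sizes are from SAP Section 2.4. One misclassified subject moves a rate by 1/46 = 2.2 percentage points in Arm A or 1/52 = 1.9 in Arm B, if all planned subjects are evaluable.

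**The case against.** The strongest reply is that the sentence has harmless readings. It may only mean that missing grades sort last when the worst grade is picked, or that a value graded in one direction of a hypo/hyper test counts as lowest in the other. The second is sound. The first makes the rule do nothing, as Step 1 shows. The text states neither limit, so the literal reading remains open to a programmer.

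The second reply is that the denominator sentence and the baseline definition already close most of the gap. This largely stands. A subject with no baseline result is outside the percentages, and an earlier valid pre-dose value serves when the latest is unusable. What remains is a subject with an assessment but no derivable grade.

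The third reply is that a specific rule may override a general one, and that the exclusion sentence in Section 3.1 holds only in general. That is fair for exclusion. The statement against imputation carries no such qualifier, and Section 3.6.7 gives no reason to depart from it.

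A reader might infer that any missed post-baseline visit hides worsening. It does not, because the maximum is unchanged. A reader might also infer a bias that nobody could detect. Section 3.1 provides listings of the original data behind the tables, and Section 3.6.7 separately summarises absolute values, changes from baseline and liver-test multiples that need no baseline grade.

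**Conclusion.** The point holds in a limited form. Followed literally, the rule gives a wrong result for a subject whose baseline grade cannot be derived, and for one with no derivable post-baseline grade despite an assessment. In both cases it conflicts with Section 3.1. The 2-grade errors described rest on reading lowest as Grade 0.

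The number of subjects is probably very small, and the SAP gives no basis for estimating it. A false 2-grade shift also needs a true baseline of at least Grade 1 and a worst grade of at least 2; a false Grade 3-4 shift needs a true baseline already at Grade 3 or 4. It would therefore be tempting, but unsupported, to infer that several subjects per arm and test are misclassified. The tables are descriptive, and Section 3.6.7 ties no test or stopping rule to them. The correction is worth making because it is cheap and removes an ambiguity, not because the safety conclusions are shown to be at risk.

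**What to change.** Replace the missing-grade sentence in SAP Section 3.6.7 with three statements:

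- For tests graded in two directions, Grade 0 is assigned in a direction only when a numeric result is present and meets no graded criterion in that direction.
- A missing baseline grade, or a wholly missing set of post-baseline grades, is not imputed; the subject appears in a Missing row or column of the shift table.
- Shift percentages use as denominator the treated subjects with a gradable baseline and at least one gradable post-baseline result for that test, and the numerator is drawn from the same subjects.

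The last statement also amends the existing denominator sentence, which refers to assessments. The cost is a short text change and one program condition. Denominators may fall by a few subjects, and those subjects would be visible in the Missing category.

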### **Assessment of Nephrotoxicity**

Creatinine clearance rate will be calculated using serum creatinine and the Cockcroft-Gault formula to estimate glomerular filtration rate (GFR). The Cockcroft and Gault formula (1973) is as follows:

- Male:  $C_{Cr} = \{((140 - \text{age}) \times \text{weight}) / (72 \times S_{Cr})\}$
- Female:  $C_{Cr} = \{((140 - \text{age}) \times \text{weight}) / (72 \times S_{Cr})\} \times 0.85,$

where  $C_{Cr}$  denotes Creatinine clearance rate (mL/minute),  $S_{Cr}$  denotes serum creatinine (mg/dL), weight (kg) denotes the weight at the current visit or the most recent visit, age in years.

Shift tables from baseline to “worst-case” on treatment  $C_{Cr}$  value will be provided. Baseline and “worst-case” on treatment  $C_{Cr}$  value will be categorized for the following categories:

- Normal:  $\geq 90$  mL/min
- Mild Impairment:  $\geq 60 - < 90$  mL/min
- Moderate Impairment:  $\geq 30 - < 60$  mL/min
- Severe Impairment:  $\geq 15 - < 30$  mL/min
- Kidney Failure:  $< 15$  mL/min

